13.1. General Aspects of Analysis

The ADAPT-PD Trial will be considered successful when the primary objective of the study is met for one or both aDBS algorithms independently or the algorithms combined.

The main analysis of the study objectives will use the Full Analysis Set (FAS) which includes all Primary Cohort subjects, using the intention-to-treat (ITT) principle, who initiate the aDBS Evaluation Phase using the randomized treatment assignment for each subject that was randomized and the programmable treatment assignment for those subjects that may only be configured to one aDBS mode (dual or single threshold).

The main analysis will include data from all contributing geographies and centers. A poolability analysis for a center effect will be performed as described in [Section 13.2.10](#).

The subjects' baseline status will be summarized with standard descriptive summary statistics, including counts and percentages for categorical variables, and mean, standard deviation for continuous variables. Safety data will be summarized as specified in [Section 13.6](#).

Subject disposition will be illustrated in a CONSORT diagram and attrition will be identified and summarized.

Medtronic Business Restricted

The handling of missing data for the primary and secondary objective is described generally in [Section 13.2.5](#) and also with each objective. Subgroup analyses are described in [Section 4.1.4](#)

13.2. General Statistical Considerations

Data analysis will be performed by Medtronic-employed statisticians or designees. A validated statistical software package will be used to analyze the study results.

Additional details of the analyses outlined in this section will be described in a separate Statistical Analysis Plan prior to the data freeze for the Primary Analysis Report. Any deviations from this section and/or the Statistical Analysis Plan will be described and justified in the Primary Analysis Report, as appropriate or in an amended CIP, if applicable.

13.2.1. Analysis sets

All-Consented (AC): includes all subjects who properly signed the study-specific informed consent (IC). This patient set will be used to summarize patient disposition.

Full Analysis Set (FAS): includes all Primary Cohort subjects, using the intention-to-treat (ITT) principle, who initiate the aDBS Evaluation Phase using the randomized treatment assignment for each subject that was randomized and the programmable treatment assignment for those subjects that may only be configured to one aDBS mode (dual or single threshold).

As-Treated (AT): includes all Primary Cohort subjects who are treated with continuous Deep Brain Stimulation (cDBS) and/or adaptive Deep Brain Stimulation (aDBS) during the cDBS Baseline Evaluation Phase and/or the aDBS Evaluation Phase, and Long-term Follow-up Phase and uses the observed treatment used for each subject in each phase.

All-Randomized (AR): includes all Primary Cohort subjects who were randomized in the aDBS Evaluation Phase, excludes those that were not configured to both modes.

Complete-Case (CC): FAS without imputation that includes all Primary Cohort subjects who have available measures for the respective analysis and are analyzed in their randomization group for those randomized or the programmable treatment for those configured to one aDBS mode.

Directional Stimulation As-Treated (DSAT): includes all Directional Stimulation Cohort subjects who have SenSight leads in a directional stimulation configuration who are treated with continuous Deep Brain Stimulation (cDBS) and/or adaptive Deep Brain Stimulation (aDBS) during the cDBS Baseline Evaluation Phase and/or the aDBS Evaluation Phase, and Long-term Follow-up Phase and uses the observed treatment used for each subject in each phase.

Directional Stimulation Complete-Case (DSCC): includes all Directional Stimulation Cohort subjects who completed the aDBS Evaluation Phase.

Medtronic Business Restricted

13.2.2. Factors That May Compromise the Outcome or Interpretation of the Results

Missing PD Home Diary Data

PD Home Diary non-compliance or incorrect completion are most concerning in the assessment of the primary effectiveness objective. PD Home Diaries will be collected, regardless of completeness or accuracy of completion. PD Home Diaries and other efficacy data collected while the subject is in the wrong treatment assignment or stimulation is inactive will be included in analyses, following [Section 13.4.5](#).

PD Home Diary compliance will be continuously monitored throughout the duration of the study to ensure that compliance is maintained.

13.2.3. Familywise error rate and hypothesis testing

The familywise error rate will be controlled using one-sided tests with an overall alpha-level of 0.025. Each primary hypothesis (one for each aDBS mode) will be assigned a Bonferroni corrected alpha (0.0125) for the respective primary hypothesis (0.025/2, see [Section 13.4.1](#)). The primary hypothesis will serve as a gatekeeper for the secondary hypothesis within each mode.

13.2.4. Sample size rationale

Since the device implant will occur outside of the study and the study requires participants to be stable on cDBS prior to enrollment, the standard deviation of the change from cDBS to aDBS in “On” time without troublesome dyskinesia will be used to establish a threshold for assessing the performance goal. The threshold will be set as 1 standard deviation. If the difference between aDBS and cDBS (aDBS-cDBS) for a subject is at least -1 standard deviation, the threshold will be met for the subject. Using this threshold, the proportion of subjects who exceed the threshold will be computed.

The sample size was estimated using a binomial distribution for a one-sided exact test (alpha=0.0125) for a proportion (PASS 2011 module Tests for One Proportion [Differences]) to compare to a performance goal of 50%. Assuming the alternative hypothesis of 85% of subjects exceeding the threshold, a minimum of 36 subjects achieves at least 90% power to reject a performance goal of 50%.

Simulations have shown that this sample size is sufficient to cover possible deviations from normality such as a uniform distribution. The threshold criterion will remain the same as the standard deviation is robust to moderate departures from normality.

Sample size in the Primary Cohort may be increased to a maximum of 55 subjects for whom at least 1 aDBS mode is acceptable and who enter the aDBS Evaluation Phase to obtain at least 8 subjects per

Medtronic Business Restricted

aDBS mode and 8 subjects per target site (STN/GPi). Criteria for increasing sample size is described in [Section 13.2.6](#).

For the safety analyses, a minimum of 30 subjects followed for approximately 30 days with aDBS out-of-clinic in the subjects' real-world environments provides at least 95% probability that all events with a true event rate of at least 10% would be reported at least once.

It is estimated that approximately 70-100 subjects implanted with a commercially available Medtronic DBS system with Percept PC INS will be enrolled in the study to obtain 40 subjects for whom at least 1 aDBS mode is acceptable and who enter the aDBS Evaluation Phase. Accounting for a 10% dropout during the aDBS Evaluation Phase, a minimum of 36 subjects (at least 8 per brain target site (STN/GPi) and 8 per aDBS mode) will complete the aDBS Evaluation phase.

In addition, approximately 15 subjects implanted with a commercially available Medtronic DBS system with Percept PC INS and SenSight system will be enrolled in the Directional Stimulation Cohort to obtain 9 subjects for whom at least 1 aDBS mode is acceptable and who enter the aDBS Evaluation Phase. Accounting for dropout during the aDBS Evaluation Phase, a minimum of 8 subjects will complete the aDBS Evaluation Phase.

13.2.5. Handling of missing data

All attempts will be made to minimize missing data. If 5% of the data or fewer are missing for the analysis, no imputation will be used.^h Otherwise, if missing data are observed, multiple imputation will be used for the analysis of the primary and secondary objectives, as described in the objective sections below. If an aDBS mode is not programmable to a subject no imputation will occur for those subjects for that aDBS mode.

Appropriate standard errors will be computed to account for the multiple imputations.^{i,j} A Complete-Case Analysis Set and As-Treated Analysis Set will be used for sensitivity analyses of the primary and secondary objective analyses.

^h Buhi, E, Goodson, P, Neilands T. Out of Sight, Not Out of Mind: Strategies for Handling Missing Data. *Am J Health Behav.* 2008 Jan-Feb;32(1):83-92, doi: 10.5555/ajhb.2008.32.1.83.

ⁱ Rubin, D. B. (1976). "Inference and Missing Data." *Biometrika* 63:581–592.

^j Rubin, D. B. (1987). *Multiple Imputation for Nonresponse in Surveys*. New York: John Wiley & Sons.

Medtronic Business Restricted

13.2.6. Interim sample size adjustment

Sample size for the Primary Cohort may be increased to a maximum of 55 subjects based on acceptability of the aDBS modes during the aDBS Setup Phase and to ensure a minimum number of subjects in each target site (STN/GPi) as described in 13.2.9.

13.2.7. Reports

Annual reports of study progress and safety data will be provided. After all aDBS treated subjects in the Primary Cohort have reached the end of their aDBS Evaluation Phase (randomized or programmable mode) a Pre-Market Approval (PMA) supplement will be submitted to request FDA approval of aDBS; a Technical Document will be submitted to request TUV approval of aDBS. These requests will include available data through the final aDBS Evaluation Phase visit and any available safety data for those subjects in the long-term follow-up phase. A final study report, which will include data covering all phases of subject follow-up, will be prepared after all subjects have completed the study.

13.2.8. Demographics and baseline variables

Demographics and baseline characteristics will be summarized for the AC, FAS, and DSCC analysis sets.

13.2.9. Pooling of aDBS mode

Most planned analyses for the Primary Cohort are to be done separately for each mode. Summary statistics will be computed to summarize the percentage who were programmed to each mode and subject characteristics of each subgroup. If fewer than 24 subjects are programmed to one of the aDBS modes because aDBS is unacceptable as compared to cDBS (using the aDBS GIC), the evaluation of aDBS effectiveness will use data from the first period of the aDBS Evaluation Phase from all subjects. If the modes are considered poolable, the modes would be combined and the alpha level of the test would be alpha=0.025 (one-sided). To test for a treatment difference in the first period by aDBS mode group, subjects will be categorized based on the modes they are programmable to: aDBS – Dual Threshold only; aDBS – Single Threshold only; and aDBS – both modes. The Freeman and Halton's extension of Fisher's exact test will be computed testing for differences between aDBS modes in the proportion of subjects exceeding threshold for the primary outcome using data only from the first period. The same categorization of mode will be used and tested using F-tests using linear regression models for the secondary outcome measure. P-values >0.1 for the tests of association with aDBS mode group will be deemed as supporting the assumption of no aDBS mode group effect and the data will be considered poolable across aDBS mode groups. If the aDBS mode group factor approaches statistical significance

(defined as ≤ 0.1),^k the data will not be considered poolable. A minimum of 8 subjects per aDBS mode will be required for the pooled analysis using the first period outcome data.

If data are pooled, missing data observed in the cDBS Baseline Phase and aDBS Evaluation Period 1 will be imputed as described in 13.2.5.

13.2.10. Center pooling

All investigators in the proposed study will conduct the study according to a common protocol and utilize the same CRFs to collect study data. Throughout the trial, efforts will be made to ensure consistency among investigative sites in selection of patients and conduct of the study procedures. In addition, site study personnel training will be conducted prior to initiation of the study at each site and periodic monitoring will be conducted by Medtronic to ensure compliance with protocol requirements.

Data will be pooled across centers for all analyses. Each study center will stop enrollment in the Primary Cohort after they have identified a maximum of 8 subjects for whom at least 1 aDBS mode is acceptable and who enter the aDBS Evaluation Phase (~25% of the total planned number of subjects). For the Directional Stimulation Cohort, each study center will stop enrollment after they have identified a maximum of 5 subjects for whom at least 1 aDBS mode is acceptable and who enter the aDBS Evaluation Phase. The actual number of subjects at a study center may be slightly larger due to the number of subjects that are enrolled prior to cessation of enrollment. This restriction is intended to reduce the possibility that the results from one study center will be overly influential in the overall study results.

Tests for a treatment difference in the Primary Cohort among centers are described in the supporting analyses of the objective sections below. When testing for differences between centers, centers with 5 or more FAS subjects will each be tested as separate centers. Those with less than 5 FAS subjects will be combined into a “pooled” pseudo-center to minimize the impact of small samples on the analysis. If the pseudo-center contains more than 50% of the subjects, the centers will be combined into more than one pseudo-center. If more than one pseudo-center is needed, the centers will be randomly ordered and divided as near the midpoint as possible. If ambiguity between assigning a center to the first or second pseudo-center exists, the center will be assigned to the first pseudo-center.

13.3. Analysis Execution

A formal analysis for the ADAPT-PD Trial will occur when all active subjects in the Primary Cohort have completed the Evaluation Phase of the study. Analysis will include both the primary and secondary

^k Fleiss JL. The statistical basis of meta-analysis. Stat Methods Med Res. 1993; 2(2):121-45.

Medtronic Business Restricted

objectives. Additional objectives will be addressed based on available data. A final report will be prepared once all data collection has ended and all subjects have completed the Long-Term Follow-up Phase or have been exited. The inferential analysis for the primary and secondary objectives will not be updated for the final report. Additional objectives will be addressed based on complete data.

13.4. Primary Objective

To demonstrate that the proportion of aDBS subjects with “On” time without troublesome dyskinesia during the Evaluation Phase exceeds a performance goal of 50%.

13.4.1. Hypothesis

Two hypotheses are being tested for the primary objective in order to compare each aDBS mode relative to cDBS at baseline, separately. The alternative hypotheses are:

- H_{11} : The proportion of subjects with “On” time without troublesome dyskinesia during aDBS dual threshold mode Evaluation Period exceeding threshold > 50%
- H_{21} : The proportion of subjects with “On” time without troublesome dyskinesia during aDBS single threshold mode Evaluation Period exceeding threshold > 50%

13.4.2. Endpoint definition

The primary endpoint is the proportion of aDBS subjects with “On” time without troublesome dyskinesia that exceed threshold. This endpoint will combine the diary categories of “On” time without dyskinesia and “On” time with non-troublesome dyskinesia. Since the device implant will occur outside of the study and the study requires participants to be stable on cDBS, the within-subject standard deviation of the change between cDBS and DBS in “On” time without troublesome dyskinesia will be used to establish a threshold for assessing the performance goal. The threshold will be set as 1 standard deviation. If the difference between aDBS and cDBS (aDBS-cDBS) for a subject is at least -1 standard deviation, the threshold will be met for the subject. Using this threshold, the proportion of subjects who exceed the threshold will be computed. The primary endpoint proportion of subjects above threshold will be compared to a performance goal of 50% using a binomial exact test. The lower bound of the 97.5% confidence limit will also be presented. Data will be imputed as described in 13.2.5 prior to computing the mean “On” time without troublesome dyskinesia for all periods when using the FAS.

Rationale for endpoint

Continuous Deep Brain Stimulation (cDBS) is a proven FDA-approved therapy in the treatment of Parkinson’s disease symptoms. This study aims to show that aDBS is a viable optional feature that can provide similar benefit and safety to cDBS for some subjects. The primary endpoint for this study compares aDBS to cDBS directly for each subject to ensure some level of consistent comparability

Medtronic Business Restricted

between cDBS and aDBS. The endpoint of PD Home Diary was chosen to determine the threshold of success as it is a measure of the subject response to DBS therapy over time, the aDBS algorithm will adapt the therapy over time, and the PD Home Diary has been used as an endpoint in previous DBS trials.

Rationale for 1 standard deviation threshold

A unit of one standard deviation was chosen as it is an acceptable amount of statistical variability in the PD Home Diary endpoint given the fluctuating nature of Parkinson's disease and the percentiles of a normal distribution.

Rationale for 50% performance goal

A performance goal of 50% was chosen for this study in order to demonstrate that at least 50% of the subjects are able to achieve the threshold with 95% confidence demonstrating some level of efficacy.

13.4.3. Sample size justification

The sample size justification for the primary objective is provided in [Section 13.2.4](#).

13.4.4. Analysis methods

The primary analysis will use the FAS as described in [Section 13.2.1](#) The PD Home Diary will be collected for at least 3 consecutive days (24 hour “periods”) prior to each visit to evaluate the primary objective. Complete diary periods collected anytime during the cDBS Baseline period will be used for analysis as subjects should be on stable cDBS stimulation from enrollment through the end of this period. In the aDBS Evaluation Phase, diary periods will be defined starting with the first completed diary record which is no more than 14 days prior to the visit. If diary is collected more than 14 days prior to the visit, the diary may be used for analysis if there is no change in aDBS stimulation settings. Complete diary periods are defined as any diary period where at least 21 hours¹ (defined as 42 30-minute records) of diary were completed during the 24-hour period, and only complete periods will be used for analysis. If the diary is collected for more than 3 complete periods, up to 7 which are closest to the visit will be used for the

¹ Neurostimulation for Parkinson's disease with early motor complications. Schuepbach WM, Rau J, Knudsen K, Volkmann J, Krack P, Timmermann L, Hälbig TD, Hesekamp H, Navarro SM, Meier N, Falk D, Mehdorn M, Paschen S, Maarouf M, Barbe MT, Fink GR, Kupsch A, Gruber D, Schneider GH, Seigneuret E, Kistner A, Chaynes P, Ory-Magne F, Brefel Courbon C, Vesper J, Schnitzler A, Wojtecki L, Houeto JL, Bataille B, Maltête D, Damier P, Raoul S, Sixel-Doering F, Hellwig D, Gharabaghi A, Krüger R, Pinsker MO, Amtage F, Régis JM, Witjas T, Thobois S, Mertens P, Kloss M, Hartmann A, Oertel WH, Post B, Speelman H, Agid Y, Schade-Brittinger C, Deuschl G; EARLYSTIM Study Group. *N Engl J Med.* 2013 Feb 14;368(7):610-22. doi: 10.1056/NEJMoa1205158.

Medtronic Business Restricted

analysis, while if a subject has zero complete periods, their diary will be considered missing. Diaries with at least 1 complete period available will be used for analysis. Data from non-contiguous complete periods may be used in the analysis.

The change in daily “On” time without troublesome dyskinesia from cDBS to aDBS will be computed for each subject. The overall standard deviation of the change will be computed for the FAS. The threshold will be set as 1 standard deviation. If the difference between aDBS and cDBS (aDBS-cDBS) for each subject is at least -1 standard deviation, the threshold will be met for the subject. Using this threshold, the proportion of subjects who exceed the threshold will be computed. The proportion with “On” time without troublesome dyskinesia during the respective aDBS Evaluation Period that exceed the threshold will be compared to the performance goal of 50% for each aDBS mode separately using a binomial exact test. The objective will be considered passed if the p-value is less than 0.0125. The lower bound of the 97.5% confidence interval will also be presented.

13.4.5. Handling of missing data

All attempts will be made to minimize missing data. If 5% of the data or fewer are missing (as defined in [Section 13.4.4](#)) for the analysis, no imputation will be used and the data will be analyzed as specified in the previous section. Otherwise, if missing data are observed, multiple imputation will be used for the analysis of the key primary objective.

Prior to the MI, the distribution of the continuous variables will be assessed for normality (using the Shapiro-Wilk test) to determine whether regression ($P \geq 0.05$) or predictive mean matching ($P < 0.05$) multiple imputation will be used for each variable. First, multiple imputation will be applied to impute missing values in continuous hours of “On” time without troublesome dyskinesia for each mode separately (aDBS single threshold, aDBS dual threshold). Variables for target site (STN or GPi) and cDBS hours of “On” time without troublesome dyskinesia will be considered for the model. The fully conditional specification (FCS) method within SAS (version 9.4 or higher) with 5 repetitions and 100 burn-in iterations will be used for imputation. No limits will be defined for imputed values. Following imputation, the “On” time without troublesome dyskinesia will be assessed against the “On” time threshold, and the estimate for the proportion of subjects meeting threshold will be determined for each imputation and combined using MI analysis methods. The lower bound of the 97.5% confidence limit will be determined from the MI Clopper-Pearson mean success approach^m. In addition, the

^m Mandan, Arpita (2018). Two Applications of Summary Statistics: Integrating Information Across Genes and Confidence Intervals With Missing Data. Master's thesis, Duke University. Retrieved from <https://hdl.handle.net/10161/17533>

Medtronic Business Restricted

objective will be tested by comparing the lower bound to 50% for each imputation, and the overall p-value will be computed as the median of the p-values from the multiply imputed datasets.ⁿ

13.4.6. Supporting analyses

Supporting analyses for the primary objective in the Primary Cohort include verifying the lack of a period or carryover effect (randomized subjects only), a target site effect (STN/GPi), a lead type effect (legacy Models 3387 and 3389 compared to SenSight Models B33005 and B33015), or a center effect.

Summarized results from the Directional Stimulation Cohort will be provided as supporting analyses to the Primary Cohort results. In addition, sensitivity analyses will be conducted using the CC and the AT Analysis Set.

An analogy of Prescott's test^o will be computed to test for a period or carryover effect and p-values >0.1 will be deemed as supporting the assumption of no period or carryover effect in the proportion of subjects exceeding threshold for the primary outcome using data from both periods. If the assumption of no period or carryover effect is accepted, target site (STN/GPi), lead type, and center pooling assessments will be made using data from all subjects treated with aDBS in the aDBS evaluation phase. If a period effect exists, only data from the first period will be used for the analysis.

To test for a treatment difference by target site (STN/GPi), lead type, and center within each mode, Fisher's exact test and Freeman and Halton's extension of Fisher's exact test, respectively, will be computed testing for differences between target sites, lead type, or centers in the proportion of subjects exceeding threshold for the primary outcome using data from both periods. P-values >0.1 will be deemed as supporting the assumption of no target site effect, lead type effect, or center effect, respectively, and the data will be considered poolable across the respective variable. If the p-value approaches statistical significance (defined as ≤ 0.1),^k the proportion exceeding threshold and the lower bound of the 97.5% confidence interval will also be estimated at each target site, lead type, or center, as applicable (eg, if the target sites (STN/GPi) do not allow for pooling the analysis will be conducted by target site for that mode.)

If center(s) causing the significance are identified, variables relating to patient characteristics and other factors will be analyzed to try to identify why this center is showing a different treatment effect.

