7.9.1.6 Supporting analyses

Supporting analyses for the primary objective in the Primary Cohort include verifying the lack of a period or carryover effect (randomized subjects only), a target site effect (STN/GPi), a lead type effect (legacy Models 3387 and 3389 compared to SenSight Models B33005 and B33015), or a center effect.

Summarized results from the Directional Stimulation Cohort will be provided as supporting analyses to the Primary Cohort results. The threshold for meeting the primary objective in the Directional Stimulation Cohort will be the same threshold as calculated for the Primary Cohort. In addition, sensitivity analyses will be conducted using the CC and the AT Analysis Set.

An analogy of Prescott’s test⁷ will be computed to test for a period or carryover effect and p-values >0.1 will be deemed as supporting the assumption of no period or carryover effect in the proportion of subjects exceeding threshold for the primary outcome using data from both periods. If the assumption of no period or carryover effect is accepted, target site (STN/GPi), lead type, and center pooling assessments will be made using data from all subjects treated with aDBS in the aDBS Evaluation Phase. If a carryover effect exists, only data from the first period will be used for the analysis.

⁵ Mandan, Arpita (2018). *Two Applications of Summary Statistics: Integrating Information Across Genes and Confidence Intervals With Missing Data*. Master's thesis, Duke University. Retrieved from <https://hdl.handle.net/10161/17533>

⁶ Ekhout, I., van de Wiel, M.A., and Heymans, M.W. (2017), Methods for significance testing of categorical covariates in logistic regression models after multiple imputation: power and applicability analysis. *BMC Med. Res. Methodol.* 17: 129. doi: 10.1186/s12874-017-0404-7

⁷ Nagelkerke, N.J.D., Hart, A.A.M. and Oosting, J. (1986), The Two Period Binary Response Cross - Over Trial. *Biom. J.*, 28: 863-869. doi:10.1002/bimj.4710280715

- [REDACTED]
- [REDACTED]
- [REDACTED]
- [REDACTED]

To test for a treatment difference by target site (STN/GPi), lead type, and center within each mode, Fisher's exact test and Freeman and Halton's extension of Fisher's exact test, respectively, will be computed testing for differences between target sites, lead type, or centers in the proportion of subjects exceeding threshold for the primary outcome using data from both periods. [REDACTED]

- [REDACTED]
- [REDACTED]
- [REDACTED]
- [REDACTED]

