7.9.2.7 Supporting analyses

Supporting analyses for the secondary objective in the Primary Cohort include verifying the lack of a period or carryover effect (randomized subjects only), tests for poolability by target site (STN/GPi), tests for poolability by lead type (legacy Models 3387 and 3389 compared to SenSight Models B33005 and B33015), and tests for poolability by center. The test for a carryover effect will use a two-sample t-test,

all other supporting analysis tests will use linear regression models. In addition, results from the Directional Stimulation Cohort will be described as a supportive analysis. The test of no period or carryover effect will be computed first, and if the assumption of no period or carryover effect is accepted, data from both periods from all subjects treated with aDBS in the aDBS Evaluation Phase will be used for the models to assess poolability by target site, lead type, and center. The models will use the change between aDBS and cDBS and include an intercept and a covariate for the respective parameter.

If the P-value is >0.1 , that will be deemed as supporting the assumption of no carryover effect and data from both periods from all subjects treated with aDBS in the aDBS Evaluation Phase will be used for the models to assess poolability by target site, lead type, and center. If a carryover effect exists (P-value ≤ 0.1), only data from the first period will be used for the analysis.

The tests for poolability of target site (STN/GPi), lead type, and center will be performed, by mode, and will include all subjects who enter the aDBS evaluation phase.

P-values >0.1 for the terms testing the effect of the respective parameters will be deemed as supporting the assumption of no target site effect, lead type effect, or center effect, respectively, and the data will be considered poolable across the respective variable. Normality of the outcome will be assessed with the Shapiro-Wilk test. If large violations to the normality assumption are observed ($p<0.05$), the

secondary endpoint may be transformed (e.g., log-transformation) or apply non-parametric method for the supporting analyses.

In addition, sensitivity analyses will be conducted using the CC and AT Analysis Sets without imputation.

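### The protocol and the SAP give different triggers for dropping second-period data, and neither says whether the rule reaches the main tests

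*Protocol*

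**What the plan says.** **Primary endpoint.** Protocol 13.4.6 and SAP 7.9.1.6 describe the same check. An analogue of Prescott's test "will be computed to test for a period or carryover effect and p-values >0.1 will be deemed as supporting the assumption" that neither effect is present. If that assumption is accepted, the target-site, lead-type and center pooling assessments use all subjects treated with aDBS in the Evaluation Phase. The sentence that follows differs:

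- Protocol 13.4.6: "If a period effect exists, only data from the first period will be used for the analysis".
- SAP 7.9.1.6: "If a carryover effect exists, only data from the first period will be used for the analysis".

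Both texts are current: the SAP's revision history says its version 4.0 is aligned with version 5.0 of the CIP. Several SAP lines after this rule are redacted.

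**TEED.** SAP 7.9.2.7 says "The test of no period or carryover effect will be computed first". It names a two-sample t-test for carryover and, at p ≤ 0.1, restricts to the first period. Protocol 13.5.7 names the same t-test and says what follows if the assumption is accepted. It does not say what follows if it is rejected.

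**Main tests.** Protocol 13.4.4 and 13.5.5 and SAP 7.9.1.4 and 7.9.2.5 use the FAS and carry no period or carryover condition.

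**The concern.** On the primary endpoint, a period effect without carryover removes the second period under the protocol and leaves it in under the SAP. No visible text says which effect has been found when the joint test gives p ≤ 0.1. On TEED, carryover removes data under the SAP, while the protocol is silent. Two analysts each following one document could analyse different data.

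Both documents restrict an analysis without saying which one. If it is the main test, the analysed data depend on a pretest of the outcome, with a nominal 10% chance of firing when neither effect exists. Each randomised subject would then count towards one mode instead of two. Under protocol 13.2.3 a mode must pass its primary test before its TEED test counts, so a loss on the first also bears on the second. If the wording is left open until outcomes are known, the rule could be chosen with results in view.

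**Working it through.** **Inputs.**

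- Primary test: "one-sided exact test (alpha=0.0125"), set "to compare to a performance goal of 50"% (protocol 13.2.4).
- Planning claim: "Assuming the alternative hypothesis of 85% of subjects exceeding the threshold, a minimum of 36 subjects achieves at least 90% power" (same section).
- TEED: difference 22, SD 35, one-sided alpha 0.0125, n = 36, at least 90% power (protocol 13.5.4, SAP 7.9.2.4).
- Allocation: two sequences in permuted blocks of two and four (protocol 9.9.3), so about half of the randomised subjects receive each mode first.
- Assumption: the number randomised is not given. All 36 completers are taken as randomised, which gives the largest share of data lost.

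**1. Primary power.** The critical count r is the smallest with P(X ≥ r | n, 0.50) < 0.0125. Power is P(X ≥ r | n, 0.85).

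| Data used | n per mode | r | attained alpha | power |
|---|---|---|---|---|
| Both periods, 36 completers | 36 | 26 | 0.0057 | 98.6% |
| First period, 36 completers | 18 | 15 | 0.0038 | 72.0% |
| First period, 40 subjects, no dropout | 20 | 16 | 0.0059 | 83.0% |
| First period, 55 subjects, no dropout | 27 or 28 | 20 or 21 | 0.0096 or 0.0063 | 96.0% or 95.1% |

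The first row reproduces the plan's figure of at least 90%.

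**2. TEED power.** One-sample noncentral t with noncentrality (22/35)√n.

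- n = 36: 0.629 × 6 = 3.77, power 91.8%, which agrees with the stated figure.
- n = 18: 0.629 × 4.243 = 2.67, power 59.0%.

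The difference of 22 is the expected decrease for dual threshold mode. For the 35 units expected in single threshold mode, with SD 35, power at n = 18 is still 95.3%.

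**3. Subjects with one acceptable mode.** They have only first-period data and lose nothing. If R of 36 are randomised and the rest split evenly (an assumption), each mode has R + (36 − R)/2 subjects with both periods and R/2 + (36 − R)/2 = 18 with the first only. For R = 24 that is 30 falling to 18, so 60% is kept instead of 50%, and primary power falls from 97.2% to 72.0%. With an uneven split, one mode keeps more than 18 and the other fewer.

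**4. Averaging over a false trigger.** With neither effect present and a firing rate of 10%:

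- Primary: 0.9 × 98.6 + 0.1 × 72.0 = 95.9%.
- TEED: 0.9 × 91.8 + 0.1 × 59.0 = 88.5%.

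This treats the pretest and the outcome test as independent, which has not been shown.

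**5. What a joint test can separate.** An assumed version was simulated: a trend test on within-subject differences with the sign reversed in one sequence, 18 per sequence, 85% success, latent correlation 0.5, 4,000 runs. At 0.1 it fired in 10% of trials with neither effect, 72% under a period shift and 71% under an equal carryover from both modes. The last two agree because both act as the same shift in period 2. Under opposite carryovers it fired in 16%, where a test on subject sums fired in 43%.

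**The case against.** The strongest reply is about scope. The sentence stands under the supporting analyses, directly after the one on pooling assessments, and SAP 7.9.2.7 likewise speaks of models for poolability. The sections defining the main tests contain no such condition. On that reading no primary or TEED power is lost. The reading is natural, but the text does not state it, and the trigger mismatch would remain. It stands as a reason to call the power figures conditional.

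Four stronger readings are tempting but unsupported:

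- *The primary pretest cannot tell period from carryover.* The visible text names one test, but redacted SAP lines may separate two, and the simulation used an assumed form of the test.
- *The same single-test criticism applies to TEED.* Both documents name a separate t-test for carryover there.
- *Randomised order makes a period effect harmless.* It protects the comparison between modes. Each main test compares a mode with an earlier, fixed cDBS baseline, so a shift in period 2 stays in the result.
- *The stated 90% power is lost for both endpoints.* That needs the wider scope, a fired rule and about 36 subjects. It fails for the primary test at 55 subjects and for the 35-unit TEED decrease.

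It can also be said that one trigger and a stated scope would suffice, and that dropping the fallback altogether is a preference. That is fair as a minimum repair. Keeping both periods is recommended because it also removes the dependence on a pretest.

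Pooling the modes at alpha 0.025 is no rescue: it is triggered by fewer than 24 subjects in a mode because of GIC unacceptability (protocol 13.2.9), not by this pretest.

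**Conclusion.** The point holds as a contradiction between two current documents. The primary endpoint has two different triggers, the TEED discard rule is in the SAP only, and the analysis to be restricted is undefined for the primary endpoint.

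The power cost is conditional. If the rule reaches the main tests and fires, with all 36 completers randomised, it is 98.6% to 72.0% for the primary test and 91.8% to 59.0% for TEED at the planning difference of 22. Half is the largest share of a mode's data that can be expected to go under balanced allocation. The share is smaller when some subjects have one acceptable mode, and first-period primary power is about 95–96% with 55 subjects all randomised and none lost. The contradiction itself rests on no assumption beyond the visible text.

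**What to change.** Put one rule in both documents:

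- Each mode's primary and TEED tests use every FAS subject's data for that mode, from whichever period it was received, whatever the pretest shows.
- Period and carryover estimates are reported descriptively.
- The first-period-only result is given as a sensitivity analysis.

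Remove or limit the discard sentence in protocol 13.4.6 and SAP 7.9.1.6 and 7.9.2.7. Protocol 13.5.7 has no discard sentence to delete, so add the matching statement there. Make the change before the data freeze for the primary report.

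The cost is wording only, with no new data. The downside is small: a real period or carryover effect would stay in the main estimate, and the sensitivity analysis would show it.
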